
Preconditions

The focus is on providing treatment to the entire family to overcome parenting challenges. Frontline practitioners and senior managers trained in the MST-CAN model. Ongoing regular supervision. Access to clinical input from therapists and psychiatris to play a role in delivering the intervention and supporting and supervising staff within the services. Staff are skilled in completing functional assessments, safety planning, and family needs assessment. Provision of services according to need, including parenting training, psychotherapy, anger management, family therapy and substance use treatment.

Research questions.

Research questions for the pilot trial are.

- **RQ1** To report on a two-armed cluster randomised pilot trial across three geographical areas in England and Wales.
- **RQ2** To measure pre-defined progression criteria to assess the feasibility for a definitive randomised controlled trial to evaluate efficacy
- **RQ3** To report on strategies to maximise recruitment and retention and how they should be implemented in a definitive study
- **RQ4** To report on the correlation between the primary outcome collected by parents and school to provide an indication of the most efficient method of collecting the primary outcome in a definitive trial for children aged less than 11 years.
- **RQ5** To report on the feasibility of collecting children's social care outcome data; rereferrals for child abuse and neglect, transitions from child protection to child in need, transitions from child protection to public law outline and/ or looked after child, child placed outside the family home, time on child protection register and recommend appropriate children's social care outcomes for a definitive trial
- **RQ6** To estimate the mean family size and the family intra-class correlation coefficient (ICC) to inform a sample size calculation for a definitive efficacy study.
- **RQ7** To estimate the pre- post-test correlation of the primary outcome measure to inform a sample size calculation for a definitive trial.
- **RQ8** To assess the quality of data completion at each assessment point to provide an indication of outcome measure redundancy.
- **RQ9** To provide an initial estimate of potential effect of MST-CAN versus BAU within 80% confidence intervals.
- **RQ10** To quantitively assess compliance with planned interventions in MST-CAN.

RQ11 To quantitively assess MST-CAN fidelity.

Success criteria and/or targets

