- 3. Usually resident in the local authority.
- 4. One parent and at least one child willing and able to provide informed consent. Consent will be taken from parents for themselves, and any child aged less than 16 years, children aged 16 years or more will provide their own consent.

Exclusion criteria

1. A child who has already been placed away from home with no prospect of reconciliation.

- 2. A child living independently.
- 3. Current actual or suspected sexual abuse involving family members.
- 4. Primary referral reason is a child's serious mental health issue.
- 5. Referred child assessed as being actively suicidal or homicidal.

Potentially eligible family referred for MST-CAN Family assessed for suitability by MST-CAN team, If ineligible family receive BAU study explained and provided with information sheet If no consent family receive Consent forms signed and BAU referred to evaluation team Evaluation team make contact and conduct baseline assessment Randomised to MST-CAN or BAU Evaluation team inform MST-CAN team and family of the allocation Evaluation team makes contact at 3 months Evaluation team makes contact at 6 months Evaluation team makes contact at 9 months and conducts follow-up assessment

Participant flow through the trial

Sample size

In the pilot study we will recruit 72 participants, 36 in each arm, across the 3 sites, with the expectation that we will successfully follow-up 58 at month 9. This will allow for exploration of key parameters needed to confirm sample size calculation for the efficacy study. It is

sufficient to allow estimation of two-sided 95% CIs around the proportions of eligible, consenting, adhering and followed-up at month 9 in each arm of the study with half-widths less than 0.15. It exceeds the 30 per group recommended by Lancaster et al (Lancaster et al., 2004) and the 35 per group recommended by Teare et al (Teare et al., 2014) for estimating the SE of a primary outcome with sufficient precision, including accounting for any variation across site, where 12 participants per arm per site is recommended.

Outcome measures

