RQ2 - We will estimate likely proportions of participants who are eligible, who consent, the proportion followed-up at 9-months, the proportion who adhere and the data completeness of primary, secondary outcomes and process outcomes. Each of these will be assessed against progression criteria agreed a priori

RQ3 – We will leverage the qualitative work planned under IPE Q2, specifically targeting retention and barriers. By conducting semi-structured interviews with 5-10 parents who initiated but did not continue the intervention, we aim to identify the underlying reasons for dropout and gather insights that could inform improvements in retention strategies. Additionally, interviews with another 5-10 parents who declined to participate will help us understand barriers to entry into the study. The data collected from these interviews will help refine recruitment techniques to enhance engagement and consent rates. We will report on strategies identified to maximise recruitment and retention from our qualitative work and where appropriate include them in the pilot study.

RQ4 - We will conduct a correlation analysis to explore the relationship between parent and school completed SDQ. First exploring the distribution of the outcome at each time-point and then selecting the appropriate parametric or non-parametric correlation approach. This will inform a decision regarding the relative utility of each approach and the source of the primary outcome for a definitive trial.

RQ5 - We will integrate questions relevant to the feasibility of collecting children's care outcome data into our interviews with 10-15 social service professionals, as planned under **IPE Q1**. These conversations will focus on current data collection practices, challenges faced, and potential areas for improvement regarding the tracking and reporting of outcomes such

as re-referrals for child abuse and neglect, transitions in child protection status, and the time on child protection plan. By tailoring these interviews to include specific questions on data management and reporting, we will gain insights into the practical aspects of data collection, which will help inform the design and implementation of robust data tracking mechanisms for the definitive trial.

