Barriers (IPE Q2)	Qualitative interviews with parents who do not consent to participate.	5-10 semi- structured interviews with parents who do not consent to intervention. Purposive sampling to obtain variety by site, family composition, gender identity, ethnicity	Transcription and inductive analysis to allow themes to emerge naturally	Explore barriers to participation in the intervention and who this occurs for	To understand how barriers to participation can be lowered or removed
Acceptability (IPE Q2), Implementation (IPE Q2) and EDI (IPE Q3)	Qualitative interviews with parents, young people, and practitioners involved in receiving/provi ding the intervention	10 parents, 10 young people, and 10 practitioners, involved in the intervention. Purposive sampling to obtain variety by site, family	Transcription and inductive analysis to allow themes to emerge naturally	Examine perspectives on intervention acceptability. Explore implementatio n successes and challenges.	Identify any potential issues with acceptability. Identify any potential modifications that can be made to

		composition, gender identity, ethnicity		Explore barriers in the reach and significance of the intervention for underrepresent ed groups	maximise the impact of the intervention. Identify any potential modifications that can be made to improve the reach and significance of the intervention for
					underrepresent ed groups
Retention (IPE Q2)	Qualitative interviews with parents who dropped out of the intervention	5-10 parents who began the intervention but dropped out. Purposive sampling to obtain variety by site, family composition, gender identity, ethnicity	Transcription and inductive analysis to allow themes to emerge naturally	Explore barriers to continued participation in the intervention	Identify any potential modifications that can be made to improve the retention of the intervention
TOTAL		50-65			

Research Methods

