The qualitative component of the study will be purposive and include interviews with 10 parents engaged in MST-CAN, 10 young people engaged with MST-CAN, 10 MST-CAN intervention delivery staff, 10-15 key stakeholders, such as child protection professionals and social care managers involved with BAU, 5-10 parents who declined involvement in MST-CAN as an intervention, and 5-10 interviews with parents who dropped out of MST-CAN intervention. These interviews will answer **IPE Q1**, **Q2**, and **Q3**. Participants will be chosen purposively to provide diversity in terms of service and age and ensure appropriate participation by gender identity and ethnicity. Although a total sample of 50 to 65 interviews

will be the aim, the sample size considerations of the qualitative component are driven by the need to achieve data saturation, and this needs to be judged in practice rather than stated in advance. Semi-structured interviews will be conducted between month 9 and month 25, either online or face-to-face, as appropriate. A research associate will interview each participant once, and within that interview we will explore each of the associated IPE research questions (see Table 3). There will be a focus on sampling diverse voices, including those from multi-agency partners, to explore equity and inclusion.

All interviews will be recorded, with consent and transcribed verbatim. Inductive thematic analysis (Braun and Clarke, 2006) will be performed on the narrative accounts, with the understanding that saturation will guide the requisite sample size, which cannot be predetermined. If saturation is not achieved, an additional 5-10 participants may be recruited. Efforts will be made to incorporate views from those who dropped out or were non-compliant with the intervention, though practical feasibility of this inclusion is a potential limitation.

The interviews aim to capture diverse perceptions of the intervention, utilising Normalisation Process Theory (Murray et al., 2010). This approach will facilitate mapping findings onto NPT's constructs: coherence (how the intervention is perceived and understood), cognitive participation (engagement and commitment of stakeholders), collective action (integration of the intervention into practice), and reflexive monitoring (ongoing assessment and adaptation of the intervention). Bracketing, reflexivity, and member checking will be integral to ensuring research trustworthiness and rigour.

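### RQ3 asks about retention in the trial, but its retention interviews sample only parents who left MST-CAN, so reasons for loss in the BAU arm have no planned family source

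*Protocol*

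**What the plan says.** The Research questions section words RQ3 at the level of the trial: "To report on strategies to maximise recruitment and retention and how they should be implemented in a definitive study". Month-9 follow-up is also a progression criterion in Table 1 (80%, 70%, 60%). The Sample size section plans to estimate it in each arm, "with the expectation that we will successfully follow-up 58 at month 9".

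Under Data analysis, RQ3 has two interview sources. For retention: "By conducting semi-structured interviews with 5-10 parents who initiated but did not continue the intervention". For recruitment: "interviews with another 5-10 parents who declined to participate will help us understand barriers to entry into the study".

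Table 3 defines the retention group in the same way as the first source. Its Retention row reads "Qualitative interviews with parents who dropped out of the intervention" and gives the sample as "5-10 parents who began the intervention but dropped out". Its Barriers row differs from the second source. The sample column says "structured interviews with parents who do not consent to intervention", while the data-collection column of the same row refers to parents who do not agree to take part. Research Methods, under Implementation and process evaluation, calls the group "5-10 parents who declined involvement in MST-CAN as an intervention".

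The other listed groups are parents and young people engaged with MST-CAN, MST-CAN delivery staff, and professionals who know BAU. The Ethics and registration section separates three kinds of withdrawal, one of which is stopping the intervention while still being followed up.

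**The concern.** The question concerns who stays in the trial, but the sample is chosen by who stays in the treatment. The two overlap only in part. A parent can stop MST-CAN and complete month 9, in which case the interview says little about trial retention. A BAU parent can be lost at month 9 without ever having started MST-CAN, in which case the plan has no route to that parent.

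This matters because participants are not blind to allocation (Randomisation section), so a BAU family knows that it will not receive the new service. Loss that differs between arms would threaten the definitive trial that this pilot is meant to inform. If BAU follow-up falls short of the Table 1 criterion, the pilot would show the shortfall but would have no planned evidence from families to explain it or to suggest a remedy.

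The varying definition of decliners is a smaller, related problem. Refusing a trial with an equal chance of either arm and refusing a therapy can have different reasons. The recruitment half of RQ3 needs the first.

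**Working it through.** **Is the interview list closed?** The groups and numbers come from Table 3 and Research Methods.

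| Group | Minimum | Maximum | Can it contain a BAU-arm family? |
|---|---|---|---|
| Parents engaged in MST-CAN | 10 | 10 | No |
| Young people engaged in MST-CAN | 10 | 10 | No |
| MST-CAN delivery staff | 10 | 10 | No (staff) |
| BAU stakeholders | 10 | 15 | No (professionals) |
| Parents who declined | 5 | 10 | No (never randomised) |
| Parents who dropped out of MST-CAN | 5 | 10 | No |
| Total | 50 | 65 | |

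Minimum: 10 + 10 + 10 + 10 + 5 + 5 = 50. Maximum: 10 + 10 + 10 + 15 + 10 + 10 = 65. This reproduces the Protocol's own 50 to 65, so the six groups use up the whole stated total. Family interviews number 10 + 10 + 5 + 5 = 30 to 10 + 10 + 10 + 10 = 40. Every one is defined by engaging with, declining or leaving MST-CAN.

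**How many BAU families are affected?** Inputs from Sample size: 72 families, 36 per arm, 58 expected at month 9.

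- Check of the planned figure: 0.80 × 72 = 57.6, which rounds to 58; and 58/72 = 80.6%.
- Expected losses: 72 − 58 = 14 families, or 14/2 = 7 per arm if losses are equal.
- BAU losses at the three Table 1 marks, 36 × (1 − p): at 80%, 36 × 0.20 = 7.2; at 70%, 36 × 0.30 = 10.8; at 60%, 36 × 0.40 = 14.4.

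So about 7 of 36 BAU families would be lost at the planned rate, about 11 at 70% and about 14 at 60%. None of them falls in a listed group.

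**Does leaving the intervention stand in for leaving the trial?** The retention sample requires that the parent began MST-CAN, and BAU parents do not. The Ethics section allows follow-up to continue after the intervention stops. The retention sample can therefore include families who were retained in the trial, and it excludes every BAU family who was not.

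**Who are the decliners?** In the participant flow, the study is explained and consent is sought before baseline and randomisation, and a family that does not consent receives BAU. Refusal in that flow is refusal of the trial. This agrees with the RQ3 analysis text. It does not agree with the sample column of the Barriers row or with Research Methods, which describe refusal of MST-CAN.

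**The case against.** The strongest reply is that RQ3 does not rest on these interviews alone. The Methods and data collection section describes set-up work with families going through child protection, listed separately from MST-CAN families, on how to engage participants and keep them in the study. It describes the interviewees in general as those participating and those who withdraw, without restriction by arm. Retention measures such as payment at each time-point and three-monthly contact are not limited to one arm. Research Methods leaves the final number of interviews to saturation and allows 5 to 10 more.

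Much of this stands, and it rules out three stronger readings that a reader might infer.

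- *That BAU retention and attitudes to randomisation cannot be learned at all.* The BAU follow-up rate will be measured. Decliners are to be asked about entry to the study, and MST-CAN interviewees were themselves randomised, so either could be asked about randomisation. No section names it as a topic, but the topic guides are not shown.
- *That the pool of MST-CAN drop-outs is too small for 5 to 10 interviews.* This would equate non-adherence with beginning and then dropping out, which the Protocol does not do. Even on that equation, 80% adherence gives 36 × 0.20 = 7.2 families, which lies within 5 to 10.
- *That all 14 expected losses could be in BAU.* Nothing in the Protocol supports such an imbalance as a forecast.

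The reply does not close the gap itself. Set-up work comes before the trial and cannot show why allocated BAU families left. The general description of interviewees assigns no numbers to BAU. The extra 5 to 10 interviews depend on saturation and are not assigned to BAU either.

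**Conclusion.** The point holds in a limited form. Followed as written, the listed interviews give RQ3 no planned family source for the reasons behind BAU-arm loss, or behind loss to follow-up as distinct from leaving MST-CAN. The size is about 7 of 36 BAU families. That figure assumes the planned follow-up of about 80% and equal loss in the two arms; at 70% or 60% follow-up in BAU it would be about 11 or 14. The conclusion also assumes that the numbered groups are what will be carried out, which their exact agreement with the stated total supports.

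The decliner definition is an inconsistency of wording between the RQ3 analysis and the Implementation and process evaluation section, and should be reconciled. It does not show that randomisation will go unexplored. Overall this is a cheap and worthwhile improvement to the pilot, not a flaw that invalidates it.

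**What to change.** Keep the 50 to 65 total and change two definitions.

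1. Redefine the Retention row of Table 3, and the matching text in Research Methods and in the RQ3 analysis, as parents in either arm who stopped MST-CAN, withdrew from the trial, or were hard to reach or lost at month 9. State that BAU families will be purposively included. I would not fix a quota, since the Protocol gives no basis for one.
2. Align the Barriers row and Research Methods with the RQ3 analysis, so that decliners are parents who declined the trial. List randomisation as one interview topic, beside data collection and MST-CAN itself.

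The cost is revised wording in the sampling frame, topic guide and ethics documents, and somewhat fewer interviews with MST-CAN drop-outs. Families lost to follow-up will be hard to interview, and the Protocol already concedes this for those who leave the intervention. The planned three-monthly contact gives the team a chance to identify hard-to-reach families in both arms before month 9.

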Families referred to MST-CAN have one or more children aged 6 to 17, subject to a Child Protection Plan for neglect, physical or emotional abuse. For some families this may be their 'last chance' before the removal of children into care. MST-CAN is delivered in home, school, and community settings at times convenient for the family, including evenings and weekends and engagement issues are viewed as the responsibility of the MST-CAN team and not the family. There is a 24-hour on-call system to respond to family crises as needed. MST-CAN aims to address risk factors through working intensively to address families' practical and therapeutic needs and create sustainable change in partnership with other services.

As the evidence base for the MST-CAN intervention in Children's Social Care is not well established in the UK we propose a pilot study to:

- Explore the feasibility of implementing and evaluating MST-CAN versus business as usual in children's social services departments.
- Explore appropriate methods to maximise recruitment and retention.
- Explore the appropriateness of parent versus practitioner versus school completion of the primary outcome.
- Explore the collection of Children's Social Care outcomes.

- Estimate the parameters needed to conduct a definitive trial.
- Estimate potential effect and cost of delivering the intervention.
- Explore acceptability, implementation, retention, and barriers to participation with a specific focus on equality, diversity, and inclusion.

To conduct a scientifically rigorous study we will conduct a randomised controlled pilot trial with randomisation stratified by the three geographical areas participating². As MST-CAN is delivered to families we propose a cluster trial with the family the unit of randomisation.

Intervention

MST-CAN

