To ensure outcomes are accessible to a wide range of potential participants we will make outcomes available in English and Welsh and provide interpreters and translations for other languages. As we anticipate a higher level of intellectual disability than the general population, we will seek the advice of specialists in how outcome tools can be presented to meet the needs of the target population; this will include using different fonts, colours, and the restriction on the amount of text presented on each page. All outcome tools will be agreed with our advisory panel prior to use and piloted with families already in receipt of MST-CAN.

Key demographic variables will be collected at baseline, these include age, sex, ethnicity, and index of material deprivation (IMD) derived from the participants postcode and converted to IMD using the IMD lookup tool:

https://geoconvert.ukdataservice.ac.uk/help/faq.html.

Primary outcome

The primary outcome will relate to the children within the family. Externalising behaviours will be assessed using the Strength and Difficulties questionnaire (SDQ; (Goodman, 1997)). This outcome is highly correlated with current and future offending behaviour. The externalising behaviour score is computed as the sum of the conduct and hyperactivity domains of the SDQ. The outcome is widely used and has demonstrated excellent validity and moderate reliability in adolescent populations (Goodman, 2001). The SDQ is suitable for self -completion by those aged 11-17 years and those with mild learning disabilities (Law and Wolpert, 2014), in the pilot study we will use the self-completed SDQ for those children aged 11 years or more and explore the correlation between parent and school reported SDQ for those aged less than 11 years. This outcome will be assessed at baseline and again at month 9.

Child related secondary outcomes

The SDQ will also be used to assess emotional symptoms and behavioural difficulties across several domains including conduct, hyperactivity, emotional regulation, peer relationships and prosocial behaviour.

For those children aged 10 or more years we will assess current delinquency using the Self-Report Delinquency Scale (SRDS; (Smith and McVie, 2003)) over the previous six months. This 19-item questionnaire has established psychometric properties (Fonagy et al., 2018) in this population and has a strong correlation (R = 0.95) with police charges (McAra and McVie, 2007).

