RQ6 – We will present descriptive statistics on family composition; number of parents, children, mean age, gender, and ethnicity. We will estimate the harmonic mean (H) of family size to incorporate into a sample size calculation by estimating the design effect.

The intra-class correlation coefficient (ICC) for the primary outcome will be estimated using the following method.

ICC or $\rho = \frac{\text{Between cluster variability}}{\text{(Within cluster variability + Between cluster variability)}}$ Using statistical notation, this is depicted as: ICC or $\rho = \frac{s_b^2}{(s_b^2 + s_w^2)}$, s_b^2 = between cluster variance s_w^2 = within cluster variance

RQ7 - We will present a descriptive analysis of outcomes, including estimates of central tendency and precision, at each time-point broken down by allocated group and site. We will examine the distribution of the primary outcome, externalising behaviours at baseline and month 9 and estimate the pre- post-test correlation using an appropriate parametric or non-parametric correlation coefficient.

RQ8 - We will present the proportion of items on each outcome designated as missing at each time-point to aid an interpretation of data redundancy, if the missing data for any outcome exceeds 40%, we will explore the utility of including the outcome in any definitive trial.

RQ9 - Inferential analysis at the pilot stage will focus on the primary outcome at month 9. After conducting diagnostic plots and selecting an appropriate regression approach, adjusting for baseline values and stratification variables as covariates, we will present the marginal effect, mean difference between the MST-CAN and BAU groups and 80% confidence intervals. This analysis will provide an estimate of potential effect and aid any decision about whether conducting a definitive study is warranted.

RQ10 - Interventions delivered as part of MST-CAN will be derived from weekly case summaries currently completed by staff involved in delivering MST-CAN, a description of interventions delivered, and adherence will be provided.

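### For children under 11, RQ4 ties the choice of primary-outcome source only to a parent-school correlation, which cannot show which source is preferable, and the protocol is inconsistent on whether practitioners are a third source

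*Protocol*

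**What the plan says.** The Research questions section sets RQ4 as follows: "To report on the correlation between the primary outcome collected by parents and school to provide an indication of the most efficient method". The sentence goes on to limit this to the under-11s. The Primary outcome section has children of 11 or more complete the SDQ themselves and, for younger children, plans to "explore the correlation between parent and school reported SDQ for those aged less than 11 years".

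The RQ4 paragraph under Data analysis names one method: "We will conduct a correlation analysis to explore the relationship between parent and school completed SDQ". The distribution is inspected first, as a basis for "selecting the appropriate parametric or non-parametric correlation approach". The stated use of the result is: "This will inform a decision regarding the relative utility of each approach and the source of the primary outcome for a definitive trial".

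On which sources are in play, the list of pilot aims at the end of the Study rationale says: "Explore the appropriateness of parent versus practitioner versus school completion of the primary outcome". Footnote 1 to Table 2 also lists parent, practitioner and school as the three sources to be compared, and gives no age limit.

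**The concern.** RQ4 asks a question of preference: which informant should supply the primary outcome for younger children in the definitive trial. The statistic named for it measures association. If parent and school scores correlate strongly, the pilot will know that they order children similarly. If they correlate weakly, it will know that they do not. In neither case does the coefficient point to one of them.

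What would help the choice is information held separately for each source: how often it is obtained at both time-points, how stable and how variable it is, whether it sits at a different level from the other, and whether it is open to reporting bias. None of this is linked to RQ4.

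The second problem is documentary. Staff reading the aims or Table 2 would expect a practitioner SDQ, possibly for children of any age. Staff reading RQ4 or the primary outcome text would expect parent and school only, for under-11s. A baseline rating that was not collected cannot be recovered after randomisation, so this has to be settled before recruitment starts.

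**Working it through.** The protocol gives no figure for RQ4, so there is none to reproduce. The check has three parts.

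**1. Can a correlation rank two sources?**

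By definition r(X, Y) = cov(X, Y) / (SD(X) × SD(Y)). Swapping X and Y leaves it unchanged, and so does adding a constant to either score. Spearman's coefficient has the same two properties.

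As an illustration, suppose both informants rate one underlying trait T with independent errors and reliabilities ρP (parent) and ρS (school). Then r(parent, school) = √(ρP × ρS), and each source correlates with the trait at √ρ. The reliabilities below are assumptions chosen to make the point; none comes from the protocol. The simulated columns use 400,000 draws per case.

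| ρP | ρS | √(ρP × ρS) | Simulated Pearson | Simulated Spearman | Parent with T | School with T |
|---|---|---|---|---|---|---|
| 0.9 | 0.4 | √0.36 = 0.60 | 0.599 | 0.581 | 0.949 | 0.632 |
| 0.4 | 0.9 | √0.36 = 0.60 | 0.599 | 0.580 | 0.631 | 0.949 |
| 0.6 | 0.6 | √0.36 = 0.60 | 0.601 | 0.583 | 0.776 | 0.775 |

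A reader given r = 0.60 cannot tell whether parent is better, school is better, or they are equal.

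**2. How many children would inform the choice?**

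The protocol does not say how many under-11s it expects. Ages 6 to 17 span 12 single years, of which 5 (ages 6 to 10) are under 11. Assuming uniform ages and one child per family:

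- baseline: 72 × 5/12 = 30
- month 9: 58 × 5/12 = 24.2, about 24

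Multi-child families or a different age mix would change these counts. Fisher intervals, tanh(atanh r ± 1.96/√(n − 3)), treating children as independent, are:

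- n = 24, r = 0.5: 0.12 to 0.75
- n = 24, r = 0.7: 0.41 to 0.86
- n = 20, r = 0.5: 0.07 to 0.77
- n = 40, r = 0.5: 0.22 to 0.70

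These intervals do not measure the defect, since symmetry holds at any sample size. They limit the remedy: pre-post correlations of 0.5 and 0.7 overlap widely at about 24 children, so a rule that picks the source with the smaller implied sample size would often be decided by noise.

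**3. Which sources does the protocol name?**

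| Place in the protocol | Sources | Age limit |
|---|---|---|
| Study rationale, list of pilot aims | parent, practitioner, school | none stated |
| Research questions, RQ4 | parent, school | under 11 |
| Outcome measures, Primary outcome | parent, school | under 11 |
| Table 2, footnote 1 | parent, practitioner, school | none stated |
| Data analysis, RQ4 | parent, school | not restated |

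No practitioner SDQ analysis is described anywhere. The opening of Methods and data collection does not resolve the matter, because it speaks of quantitative data from parents and children only.

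**The case against.** The best defence is that the protocol claims little. The correlation is to inform a decision and provide an indication, and Data analysis opens by promising a synthesis of quantitative and qualitative data. A reader might infer that the plan commits to choosing the source from the coefficient alone. The wording does not go that far, and that reading should not be pressed.

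A second defence reads efficiency operationally: if the two sources agree well, use the one that is easier to obtain. This has some force, and a high correlation is relevant to it. But a high correlation can coexist with a systematic difference in level, which matters if one source is ever allowed to stand in for the other. Nor does RQ4 tie any measure of ease or completeness by source to the choice. A low correlation gives no direction at all.

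A third defence is that neighbouring research questions supply the missing pieces. RQ6 gives the ICC, RQ7 the descriptive statistics and pre-post correlation, RQ9 the adjusted difference, and RQ8 the missingness: "We will present the proportion of items on each outcome designated as missing at each time-point to aid an interpretation of data redundancy". These are the right kinds of quantity, but as written none is split by informant or linked to RQ4. A SAP, which is not available here, could add the split. It would not by itself mend a protocol that pairs a ranking question with a non-ranking statistic, or settle two sources against three.

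Two further inferences go beyond the text. One is that the whole primary outcome is at stake; in fact older children self-complete and only the under-11s are affected. The other is that practitioner ratings will be collected and left unanalysed, or planned and never collected. The protocol shows an inconsistency and does not say how it will play out.

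**Conclusion.** The point holds in a limited form. For children under 11, the only analysis that RQ4 names is one that cannot distinguish the candidate sources, and no other by-source measure is attached to the decision. This follows from the definition of a correlation and does not rest on any assumed value.

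The practical size cannot be stated from the protocol. Translating differences in pre-post correlation into a ratio of required sample sizes is tempting, but the correlations would have to be invented, and the protocol does not say that efficiency means smallest sample size. The counts of about 30 children at baseline and 24 at month 9 rest on uniform ages and one child per family. They serve only to show that by-source estimates will be imprecise.

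The conflict over the practitioner source and the missing age limit in the Table 2 footnote are plain on the face of the text. The pilot can run as it stands, but the RQ4 analysis does not answer the RQ4 question. The change should be made, and the reconciliation is needed before baseline collection.

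**What to change.** In RQ4, keep the parent-school correlation as description and add, for under-11s:

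- for parent and school separately, completeness of the SDQ externalising score at baseline and month 9
- for each source, the pre-post correlation and the SD
- the mean parent-school difference with limits of agreement

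Give all estimates with intervals, because the subgroup is small. State that the choice of source will weigh these results together, along with possible reporting bias from parents, since families know their allocation. Do not adopt a mechanical rule that selects the source with the smallest implied sample size: it would rest on few children and would ignore that bias.

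Separately, make the list of aims, RQ4, the Primary outcome section, Table 2 footnote 1 and the RQ4 analysis agree on the sources and the age limit before baseline collection starts.

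The cost is a few extra tabulations of parent and school data already planned. Deleting the practitioner source costs nothing; keeping it means collecting those ratings and writing an analysis for them.
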